14.2.1 Protocol Deviation Process

Investigators must report protocol deviations to the Sponsor within 5 working days of investigational site knowledge of the deviation by entering data into the eCRF. Any protocol deviations that affect the rights, safety or well-being of the subject or the scientific integrity of the clinical investigation, including those which occur under emergency circumstances must be reported within 24 hours to the Sponsor and IRB, if required by the IRB, or national regulations.

14.3 Corrective/Preventive Action

Deviations from clinical protocol requirements will be reviewed and evaluated on an ongoing basis and, as necessary, appropriate corrective actions will be put into place to bring a site into compliance.

14.4 Study Audit(s)

Audits may be performed as deemed necessary by Cheetah Medical, in a manner consistent with applicable procedure.

14.5 Study Registration

A description of this trial will be available on www.clinicaltrials.gov, the U.S. approved clinical trial registry site.

15. ETHICS/PROTECTION OF HUMAN SUBJECTS

15.1 Statements of Compliance

This study will be performed in accordance with Good Clinical Practice Guidelines, the Code of Federal Regulations Title 21 CFR Parts 50, 54, and 56.

The clinical investigation shall not begin until the required approval/favorable opinion from the Institutional Review Board (IRB) has been obtained including approval of the Informed Consent Form to be used with subjects.

Any additional requirements imposed by the IRB shall be followed.

15.2 Institutional Review Board

Each participating institution must provide for the review and approval of this protocol and the associated informed consent documents by an appropriate Institutional Review Board (IRB) prior to subject enrollment. Any amendments to the protocol or changes to the informed consent document must also be approved before they are placed into use. The Investigator should notify the IRB of deviations from the protocol and SAEs occurring at the site in accordance with local procedures. The Investigator is responsible for continued study related communication with the IRB, including submission of study report and SAE notifications as per local regulatory requirements.

15.3 Informed Consent Process

Informed consent is a process that is initiated prior to the individual's agreeing to participate in the study and continues throughout the individual's study participation. Extensive discussion of risks and possible benefits of this therapy will be provided to the subjects (and their families, as applicable). Consent forms describing in detail the study interventions/ products, study procedures, and risks are given to the subject and written documentation of informed consent is required prior to starting any study-specific tests or intervention /administering of study product.

Consent forms will be approved by the IRB and the subject will be asked to read and review the document. Upon reviewing the document, the site investigator or designated study personnel will explain the research study to the subject and answer any questions that may arise. The subject (or their authorized legal representative) will sign the informed consent document prior to any procedures being done specifically for the study. The subject should have the opportunity to discuss the study with their surrogates or think about it prior to agreeing to participate, unless study timeframes do not allow for such discussions. The subjects may withdraw consent at any time throughout the course of the trial. A copy of the informed consent document will be given to the subjects for their records. The rights and welfare of the subjects will be protected by emphasizing to them that the quality of their medical care will not be adversely affected if they decline to participate in this study.

Modifications to the study informed consent must have approval from the Sponsor and the EC as required.

15.4 Subject Confidentiality

Confidentiality of data shall be observed by all parties involved at all times throughout the clinical investigation. All data shall be secured against unauthorized access. Sites will maintain subject privacy in accordance with local and national regulations and institutional requirements including all applicable provisions of the Health Insurance Portability and Accountability Act (HIPAA) and its current regulations.

Subjects must be identified only by their assigned study number and initials on all CRFs and other records and documents submitted to the Sponsor, the monitor, and other authorized parties. The Investigator should maintain a Subject Identification List with complete identification information (name, address, contact number, informed consent version number) on each subject. Documents not required to be submitted to the Sponsor such as subject written informed consent form, should be maintained by the Investigator in strict confidence.

The privacy of each subject and confidentiality of his/her information shall be preserved in reports and when publishing any data. The principal investigator or institution shall provide direct access to source data during and after the clinical investigation for monitoring, audits, IRB review and regulatory authority inspections. As required, the principal investigator or institution shall obtain permission for direct access to source documents from the subject, hospital administration and national regulatory authorities before starting the clinical investigation.

16. PROTOCOL AMENDMENTS

The clinical protocol, eCRFs, ICF and other subject information, or other clinical investigation documents shall be amended as needed throughout the clinical investigation, and a justification statement shall be included with each amended section of a document. Proposed amendments to the protocol shall be agreed upon between the Sponsor and Principal Investigator, or the Coordinating Investigator. The amendments to the protocol and the subject's informed consent form shall be notified to, or approved by, the IRB as required. For non-substantial changes [e.g. minor logistical or administrative changes, change of monitor(s), telephone numbers, renewal of insurance] not affecting the rights, safety and well-being of human subjects or not related to the clinical investigation objectives or endpoints, a simple notification to the IRB can be sufficient. The version number and date of amendments shall be documented.

17. TERMINATION OF STUDY OR STUDY SITE PARTICIPATION

The Sponsor may terminate the study at any time. If the study is terminated prior to the completion of expected enrollment for any reason, all participating centers will be notified within five working days. All subjects already enrolled will continue to be followed for the planned course of study described in this protocol. The study shall be terminated following the last enrolled subject.

The Sponsor reserves the right to terminate study site participation and remove appropriate study materials at any time. Specific instances that may precipitate such termination include but are not limited to the following:

- Failure to meet minimum subject enrollment requirements
- Failure to comply with protocol specified procedures and documentation
- Failure to comply with regulatory regulations
- Failure to comply with Good Clinical Practice

The site Investigator may also discontinue study participation with suitable written notice to the Sponsor.

18. PUBLICATION POLICY

Specifics of the publication policy will be outlined in the Clinical Trial Research Agreement.

APPENDIX A- TREATMENT ALGORITHM

[figure not shown]

# 1 ABBREVIATIONS

Abbreviation	Definition
AE	Adverse Event
AKI	Acute Kidney Injury
CEC	Clinical Events Committee
CPsup	Conditional Power to Claim Superiority
CRF	Case Report Forms
CSR	Clinical Study Report
DMC	Data Monitoring Committee
FDA	United States Food and Drug Administration
FRESH	Fluid Responsiveness Evaluation in Sepsis-associated Hypotension
ICU	Intensive Care Unit
IRB	Institutional Review Board
ITT	Intent-To-Treat Population
MITT	Modified Intent-To-Treat Population
PLR	Passive Leg Raise
PP	Per-Protocol Population
RRT	Renal Replacement Therapy
SAE	Serious Adverse Event
SAP	Statistical Analysis Plan
SOP	Standard Operating Procedure
SSR	Sample Size Re-estimation
SV	Stroke Volume
SVI	Stroke Volume Index
TEAE	Treatment Emergent Adverse Event

## 2 SUMMARY

TITLE	Evaluation of fluid volume in patients with sepsis and refractory hypotension.
PREFACE	
This Statistical Analysis Plan (SAP) describes the planned analysis and reporting for Cheetah Medical, Inc. protocol PRO-0001 (Fluid Responsiveness Evaluation in Sepsis-associated Hypotension [FRESH] Fluid Trial). This study is being completed to assess the safety and efficacy in using Starling SV for dynamic assessment of fluid responsiveness in the treatment of septic patients with refractory hypotension.
 
The following documents were reviewed in preparation of this SAP:
 
 
• Clinical Research Protocol PRO-0001, issued 30OCT2017
 
• Case report forms (CRFs) issued 01DEC2017 for Protocol PRO-0001
 

PURPOSE	The purpose of this SAP is to outline the planned analyses in support of the Clinical Study Report (CSR) for protocol PRO-0001. Exploratory analyses not necessarily identified in this SAP may be performed to support the clinical development program. Any post-hoc, or unplanned, analyses not identified in this SAP will be clearly identified in the respective CSR or manuscript.
STUDY OBJECTIVES	The objective of this study is to assess the mean difference in fluid balance at 72 hours or ICU discharge, whichever occurs first, and associated patient outcomes, based on a dynamic assessment of fluid responsiveness in septic patients with refractory hypotension in an ICU setting.
STUDY ENDPOINTS	
Primary: Fluid balance (L) at 72 hours or ICU discharge, whichever occurs first
 
Secondary:
 
 
1. Changes in serum creatinine level from baseline to 72 hours (key secondary endpoint)
 
2. Requirement for renal replacement therapy (RRT)
 
3. Requirement for ventilator use
 
4. Length of ICU stay (days) until subject is medically ready for discharge
 
5. Number of hours with ventilator use (30-day period)
 
6. Number of hours with vasopressor use
 
 
Not for Formal Testing:
 
 
1. Incidence of Adverse Events (AE)
 
2. Number of ICU readmissions
 
3. 30 day in-hospital Mortality rate
 
4. Volume of Treatment Fluid
 
5. Incidence of MACE
 
6. Discharge location
 
7. Mean difference in fluid balance at ICU discharge
 

STUDY DESIGN	This study is a prospective, multi-center, randomized trial comparing the mean difference in fluid balance and associated patient outcomes between a treatment guided by a dynamic assessment of fluid responsiveness and a standard of care control group not using dynamic fluid assessment.

	
Subjects will be randomized in a 2:1 treatment to control group ratio to increase power for sub-analysis by patient population. Subject randomization will be stratified by time window of enrollment to ensure even randomization between the three time windows of enrollment (0-6 hours, 6-12 hours, and 12-24 hours).
 
Patients randomized to the Starling SV arm will have treatment guided by a dynamic assessment of fluid responsiveness (measured by a change in stroke volume index > 10%) as assessed by passive leg raise (PLR).
 
Patients randomized to the control group will receive standard of care treatment. The use of dynamic fluid assessment (i.e. SVV, PPV, or SV change) to determine fluid responsiveness within the control group is prohibited.

INTERIM ANALYSES	
An interim analysis is planned after 90 subjects have been enrolled and completed the evaluation of the key secondary endpoint of change in serum creatinine at 72 hours. At this analysis, a sample size re-estimation will occur in order to determine promise for superiority in the key secondary endpoint.
 
No annual reports for the FDA are anticipated prior to the end of data collection as this study is not intended to support a regulatory filing.
 
An annual report and project status update may be requested by the local IRB at study sites.
 
No other interim analyses are planned.

FINAL ANALYSES	
All final planned analyses identified in this SAP will be completed after the last subject has completed their 30 day follow up.

## 3 SEQUENCE OF PLANNED ANALYSES

### 3.1 INTERIM ANALYSES

#### *3.1.1 INTERIM ANALYSES FOR SAMPLE SIZE OF SECONDARY ENDPOINT SUPERIORITY*

The trial will incorporate a sample size re-estimation (SSR) at the time of the interim look based on promise for superiority in the key secondary endpoint of change in serum creatinine from baseline to 72 hours. The maximum enrollment being considered for this trial is 210 total enrolled ( $N_{\max} = 1.75$  times  $N_{\min} = 120$ , where the sample size of 120 is determined as noted in Section 5 below).

The interim analysis on the key secondary endpoint incorporating a SSR will take place when 90 subjects have been enrolled and completed the key secondary endpoint evaluation. The interim analysis will be performed by an independent statistician. It is assumed that the acute endpoint assessments will be fully informed at the time of the interim analysis.

**There will be no inspection of the primary study endpoint at this interim stage. The primary study endpoint will be tested as final at the formal planned final sample size of 120 patients and will not incorporate an alpha spent. In the event of an SSR due to the key secondary endpoint, the primary endpoint will be tested again at the final sample size. No alpha-adjustment is needed across this potential multiple testing of the primary endpoint since the primary endpoint will need to be met at both  $N_{\min}=120$  and, if the sample size is increased to  $>120$ , at the final sample size.**

After 90 patients have completed the secondary endpoint, the conditional power to claim superiority ( $CP_{\text{sup}}$ ) on the key secondary endpoint for change in creatinine level from baseline to 72 hours will be computed assuming a planned final sample size of 120 patients. The conditional power ( $CP_{\text{sup}}$ ) will be calculated based on the observed interim results of the key secondary endpoint, with the specific interest of demonstrating superiority of the experimental treatment versus the control. The data will be partitioned into three zones based on  $CP_{\text{sup}}$  unfavorable zone ( $CP_{\text{sup}} < 50\%$ ), promising zone ( $50\% \leq CP_{\text{sup}} < 80\%$ ), and favorable zone ( $CP_{\text{sup}} \geq 80\%$ ). If  $CP_{\text{sup}} < 50\%$  or  $CP_{\text{sup}} \geq 80\%$  the study will continue as is. If  $50\% \leq CP_{\text{sup}} < 80\%$  then the sample size may be increased (to a maximum of 210 total) to yield 80%  $CP_{\text{sup}}$  without increasing Type I error, following the methodology of Chen, DeMets and Lan (2004).

#### *3.1.2 ANNUAL REPORTS*

As this study is not designed to support regulatory filings, no annual reports are anticipated at this time. Annual project updates may be provided at the request of site IRBs.

### 3.2 FINAL ANALYSES AND REPORTING

All final, planned, analyses identified in the protocol and in this SAP will be performed only after the last subject has had 30-day follow-up. Key statistics and study results will be made available to Cheetah Medical, Inc. following database lock. Any post-hoc, exploratory analyses completed to support planned study analyses, which were not identified in this SAP, will be documented and reported as necessary. Any results from these unplanned analyses will also be clearly identified as post-hoc analyses.

## 4 STUDY OBJECTIVES AND ENDPOINTS

### 4.1 STUDY OBJECTIVE

The objective of this study is to assess the mean difference in fluid balance at 72 hours or ICU discharge, whichever occurs first, and associated patient outcomes, based on a dynamic assessment of fluid responsiveness in septic patients with refractory hypotension in an ICU setting.

### 4.2 STUDY ENDPOINTS

#### 4.2.1 PRIMARY ENDPOINT ANALYSIS

The primary endpoint analysis is an evaluation of the difference (L) between the two treatment groups' mean fluid balance at 72 hours or ICU discharge, whichever occurs first. The following are the null and alternative hypotheses:

$$H_0: \mu_c - \mu_t = 0$$

$$H_a: \mu_c - \mu_t \neq 0$$

where  $\mu_t$  and  $\mu_c$  are the average fluid balance in the Starling SV and control groups, respectively.

#### 4.2.2 SECONDARY ENDPOINTS

##### 4.2.2.1 For formal testing

Key secondary endpoints for the purposes of formal statistical testing are:

- Changes in serum creatinine level from baseline to 72 hours (key secondary endpoint)
- Requirement for renal replacement therapy (RRT)
- Requirement for ventilator use
- Length of ICU stay (days) until subject is medically ready for discharge
- Number of hours with ventilator use (30-day period)
- Number of hours with vasopressor use

#### 4.2.2.2 Not for formal testing

Additional exploratory secondary endpoints identified for testing, but will not be included in the formal statistical testing procedures for key secondary endpoints are:

- Incidence of Adverse Events (AE)
- Number of ICU readmissions
- Mortality rate
- Volume of treatment fluid
- Incidence of Major Adverse Cardiac Event (MACE)
- Discharge location
- Mean difference in fluid balance at ICU discharge

## 5 SAMPLE SIZE

Subjects will be randomly assigned in a 2:1 ratio to treatment with Starling SV or to treatment with standard of care, stratified by time window of enrollment (0-6 hours, 6-12 hours, and 12-24 hours). The primary effectiveness endpoint for this study is fluid balance at ICU discharge.

Minimum enrollment ( $N_{\min}$ ) in the study will be set at 120 subjects (80 Starling SV and 40 control) to power at 80% for demonstration of superiority of means for the secondary endpoint of creatinine levels as a measurement of change from baseline at 72 hours. The secondary endpoint for change in creatinine levels at 120 evaluable subjects displays 80% power at a two-sided alpha level of 0.05 to demonstrate superiority of Starling SV under an assumption of an average treatment effect of -1.4 mg/dL with a standard deviation of 2.5 mg/dL.

Under an assumption of an average treatment effect of -2 L with a standard deviation of 3 L, the sample size of 120 evaluable subjects provides 92.7% power in a test of superiority of means for the primary effectiveness endpoint at a two-sided 0.05 level of significance.

The trial will incorporate a sample size re-estimation (SSR) at the time of the interim look (after 90 patients have been evaluated for the key secondary endpoint) based on promise for superiority in the key secondary endpoint. Sample size re-estimation, described in further detail in Section 3.1, will result in a maximum of 210 total evaluable subjects, or no more than 1.75 times the minimum of 120.

## 6 ANALYSIS POPULATIONS

### 6.1 ALL ENROLLED

Any subject who has signed informed consent will be included in the all enrolled population. Should a subject be considered a screen failure, the reason for failure will be documented and the subject will be exited from the study.

### 6.2 INTENT TO TREAT POPULATION (ITT)

The intent-to-treat (ITT) population for this study includes subjects that are enrolled in the study, have signed the ICF, meet study eligibility criteria, and have been randomized to either the treatment or control arm of the study.

### 6.3 MODIFIED INTENT TO TREAT POPULATION (MITT)

Subjects will be included in the Modified Intent-to-Treat (mITT) group if they sign the ICF, meet study eligibility criteria, are randomized, and in the treatment group receive monitoring for the first 72 hours of study enrollment or until ICU discharge, whichever occurs first. The mITT population will be conducted as a supportive analysis population for the primary and secondary endpoints.

### 6.4 PER-PROTOCOL (PP)

Subjects will be included in the Per-protocol group if they sign the ICF, are randomized and have the assigned procedure completed, meet critical study eligibility criteria and have no major protocol deviations (to be pre-defined as an attachment to the interim and final analyses), and, in the treatment group, receive monitoring for the first 72 hours of study enrollment. The PP population represents the primary analysis population for the primary and secondary endpoints.

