12.2.3 Modified Intent-to-Treat (mITT)

Subjects will be included in the Modified Intent-to-Treat group if they sign the ICF, meet study eligibility criteria, are randomized, and in the treatment group receive monitoring for the first 72 hours of study enrollment or until ICU discharge, whichever occurs first. The mITT population represents the Primary and Secondary Analysis population for this study.

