12.2.4 Per-Protocol (PP)

Subjects will be included in the Per-protocol group if they sign the ICF, are randomized and have the assigned procedure completed, meet critical study eligibility criteria and have no major protocol deviations (defined in the Statistical Analysis Plan), and, in the treatment group, receive monitoring for the first 72 hours of study enrollment. The PP population represents a subgroup analysis population for this study.

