# 9 EFFICACY ANALYSES

All efficacy analyses will be performed on the PP analysis population (primary) and mITT analysis population (supportive).

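### The SAP makes per-protocol the primary efficacy set where the protocol names mITT; both sets filter only the device arm after randomisation, and no efficacy analysis is assigned to all randomised patients

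*SAP*

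**What the plan says.** **Which set is primary.** Protocol 12.2.3: "The mITT population represents the Primary and Secondary Analysis population for this study". Protocol 12.2.4: "The PP population represents a subgroup analysis population for this study". The SAP reverses this. Section 6.4 reads "in the treatment group, receive monitoring for the first 72 hours of study enrollment. The PP population represents the primary analysis population", section 6.3 calls mITT supportive, and section 9 states: "All efficacy analyses will be performed on the PP analysis population (primary) and mITT analysis population (supportive". None of these sections says that it departs from the protocol. SAP 6.5 does say so for its change to the safety set.

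**The monitoring condition.** For mITT, SAP 6.3 requires that subjects "in the treatment group receive monitoring for the first 72 hours of study enrollment or until ICU discharge, whichever occurs first". PP carries the same device-arm condition without the ICU-discharge alternative. The protocol words both sets the same way. Neither set has a monitoring condition for controls.

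**ITT.** SAP 6.2 limits it to subjects who "have signed the ICF, meet study eligibility criteria, and have been randomized to either the treatment or control arm of the study". The SAP uses ITT for disposition (7.2), protocol violations (7.4) and as the base of the safety set (6.5).

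**Major deviations.** Protocol 12.2.4 excludes from PP anyone with a major deviation, the condition being "no major protocol deviations (defined in the Statistical Analysis Plan". SAP 6.4 says the list is "to be pre-defined as an attachment to the interim and final analyses".

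**The concern.** Two problems are separate and should be kept apart.

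The first is a contradiction. The two documents name different primary sets, so the headline result depends on which one is followed.

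The second is a design fault that either choice leaves in place. Completing 72 hours of monitoring happens after randomisation and may depend on how the patient is doing. Applying it to one arm means the patients compared are no longer the groups that were randomised. PP is the sharper case. The primary endpoint is measured at 72 hours or ICU discharge, whichever is earlier (SAP 9.1). Read literally, PP nevertheless removes a device patient who leaves the ICU and stops monitoring before 72 hours, although that patient has a valid endpoint. A matching control is not removed on that ground. Monitoring may continue on another unit (protocol inclusion 4), so this applies only where it stops.

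The primary result gates every formal secondary test (SAP 7.5), so the choice of set affects all confirmatory claims.

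**Working it through.** **1. The texts side by side**

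| | Protocol | SAP |
|---|---|---|
| Primary efficacy set | mITT (12.2.3) | PP (6.4, 9) |
| Other set | PP, subgroup (12.2.4) | mITT, supportive (6.3, 9) |
| Monitoring condition, device arm | mITT: 72 h or ICU discharge; PP: 72 h | same |
| Monitoring condition, controls | none in either set | none in either set |
| Efficacy analysis assigned to ITT | none | none |
| Major deviations | said to be in the SAP (12.2.4) | deferred to an attachment (6.4) |

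The sensitivity analyses of SAP 9.1 and the conditional imputation of SAP 7.3 name no population. Protocol 12.6 treats subjects without 72 hours of monitoring as missing and names no arm; the SAP does not restate this rule.

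ITT as worded is not a clean fallback. It requires eligibility, and two exclusions in protocol 8.3 can be judged only after randomisation: item 12 (treatment not started within an hour of randomisation) and item 26 (treatment departing from the algorithm). Protocol 7.2 gives controls no required treatment protocol, so item 26, and the adherence clause in inclusion 4, can in effect be failed only in the device arm.

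**2. The plan's own power figure**

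Inputs from SAP 5: 80 and 40 patients, effect -2 L, SD 3 L, two-sided 0.05. Standard error = 3 × √(1/80 + 1/40) = 0.581 L. Noncentrality = 2/0.581 = 3.44 on 118 df. Power from the noncentral t is 92.7%, as stated.

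**3. Bias from a one-arm filter**

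Let f be the fraction of the device arm removed, K the mean of those kept and D the mean of those removed. The whole-arm mean is (1 − f)K + fD = K + f(D − K). The kept mean therefore differs from the whole-arm mean by −f(D − K). The control mean does not move, so this is the bias in the treatment difference.

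**4. Illustration: no true effect, removed patients higher**

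Both f and D − K are assumed. Whole-arm SD is 3 L, controls are unfiltered, and the test is a pooled t-test at two-sided 0.05 (200,000 simulated trials per scenario). False superiority means significant with the lower mean in the device arm; its nominal rate is 2.5%.

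| Removed | Bias, D − K = 2 L | False superiority, 80 kept | False superiority, removed out of 80 | False superiority, D − K = 1 L, 80 kept |
|---|---|---|---|---|
| 5% | -0.10 L | 3.7% | 3.7% | 3.0% |
| 10% | -0.20 L | 5.4% | 5.3% | 3.7% |
| 15% | -0.30 L | 7.7% | 7.4% | 4.5% |
| 20% | -0.40 L | 10.6% | 10.1% | 5.3% |

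Hand check of the 20% row, 80 kept: 0.40/0.581 = 0.689, and the noncentral t beyond 1.980 gives 10.1%. The simulated 10.6% is slightly higher because fixing the whole-arm SD at 3 L makes the kept patients' SD √(9 − 0.2 × 0.8 × 2²) = 2.89 L.

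**5. Illustration in the other direction: true effect -2 L, removed patients 1.5 to 2 L lower**

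| Removed | Estimate | Power, 80 kept | Power, removed out of 80 |
|---|---|---|---|
| 10% | -1.85 to -1.80 L | 89–87% | 88–86% |
| 25% | -1.625 to -1.50 L | 80–75% | 76–70% |

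These compare with 92.7%. If removed patients do not differ from the rest, there is no bias in either direction.

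**The case against.** The mITT/PP contradiction is hard to dispute. The stronger objections concern what follows from it.

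- **An unnamed population is not an absent one.** SAP 7.3 lists non-adherence as a cause of missing data and imputes if more than 5% of subjects lack primary data. That could be read as restoring the filtered patients. It is a possible reading, but the analysis is conditional and names no set, while SAP 9 sends all efficacy analyses to PP and mITT. The exact statement is that no efficacy analysis is assigned to all randomised patients.
- **The ITT wording is inconsistent rather than plainly selective.** SAP 7.4 tabulates eligibility violations within ITT, and SAP 6.5 implies that ITT can contain patients never started. This stands. Removal under exclusions 12 and 26 is one reading, and the treatment algorithm in Appendix A is not in the text available to confirm it. Likewise, protocol 9.2 does not say whether withdrawal for an unusable device signal falls before or after randomisation.
- **The losses will be visible.** SAP 7.2 reports set sizes, withdrawals by arm with reasons, and a flow chart. A reader will see how many were removed, but not from this what their outcomes were, and the bias needs both.
- **The sizes are assumed.** Both documents expect little missing data. At 5% removed, false superiority is 3.0–3.7%. The larger fractions have no basis in the documents. The power figures with 80 kept also carry the small SD reduction shown above: with SD held at 3 L, the 25% and 2 L case gives 72.6%, not 75%.
- **Context.** The SAP says the study is not meant for a regulatory filing, and the deviation list may exist as a separate attachment. Neither point settles which set is primary.

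**Conclusion.** The concern holds. The contradiction over the primary set, the missing ICU-discharge alternative in PP and the one-arm condition in both sets are in the text and need no assumption. That the change is unmarked refers to the text supplied: the SAP cites a protocol issued 30OCT2017, and the version of the protocol reviewed cannot be confirmed.

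The size of any bias is not known. It rests on two quantities the documents do not give, and it could favour or disfavour the device. The tables show that bias is possible, not how large it will be. The documents must be reconciled whichever set is chosen. Making all randomised patients primary goes beyond both documents, but it is the only choice here that removes selection after randomisation.

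**What to change.** 1. **SAP 6.2, 6.4 and 9:** name one primary efficacy set: *all randomised patients, analysed in the arm assigned, whether or not monitoring was started or completed*.
2. **Exclusions from that set:** allow only facts fixed before randomisation and applied alike in both arms, such as dialysis at entry or chronic dialysis (SAP 9.1). State that exclusions 12 and 26, the adherence clause of inclusion 4, any post-randomisation withdrawal under protocol 9.2 and the lost-to-follow-up categories of protocol 8.7.1 do not remove a patient. Assign the SAP 7.3 imputation analysis to this set.
3. **mITT and PP:** keep them as supportive. Word any monitoring or completeness condition identically for both arms and include the ICU-discharge alternative. Such a condition is still selection after randomisation, so it must not define the primary set.
4. **Reconcile** with protocol 8.7.1, 9.2, 12.2 and 12.6, and mark any remaining change as SAP 6.5 does.
5. **Major deviations:** put the list in the SAP before the interim analysis. That look covers creatinine only (SAP 3.1.1), so the interim exposure is limited to the key secondary endpoint.

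**Cost.** The change is mostly wording, plus recording fluid balance to 72 hours or ICU discharge after monitoring stops. There is also a power cost if unmonitored device patients gain nothing. The effect becomes -2 × (1 − u) L, where u is the fraction unmonitored, with 80 against 40 and SD 3 L as in SAP 5:

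| u | Effect | Power at 120 | 2:1 total to regain 92.7% |
|---|---|---|---|
| 5% | -1.9 L | 90.0% | 135 |
| 10% | -1.8 L | 86.7% | 150 |
| 20% | -1.6 L | 78.0% | 189 |
| 30% | -1.4 L | 66.6% | 243 |

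Power stays at about 80% or more up to roughly 18% unmonitored. The last total exceeds the maximum of 210. If losses are as low as both documents expect, the cost is small.
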